13.0 Early Termination Visit Procedures

If a subject wishes to end his/her participation in the study prematurely, whether because of an AE or any other reason, he/she should be asked to complete a termination visit at the next scheduled appointment or within 14 days, whichever is more convenient. The investigator should make every reasonable attempt to perform the final assessment. Whenever possible, all final visit procedures should be performed at the time of an early termination visit. All outstanding AEs should be followed to resolution or stability. The reason for early termination should be clearly stated in the source and data collection tool.

All adverse events that result in a subject's withdrawal from the study must be reported to the Project Manager of Clinical Investigation, [name], BSN [contact] cell), within 24 hours.

14.0 Safety

14.1 Definition of Adverse Event

An AE is any untoward or unexpected medical occurrence in a subject participating in a clinical study whether or not there is a possible relationship between the investigative agent and the event and regardless of whether or not the subject has received any study product. Once a patient signs an informed consent document, he/she becomes a study subject and AE data will

be collected from that point until the end of the study or 30 days after the last dose of study product, whichever is longer. An AE may be an untoward, unintended or unexpected sign, symptom, disease or worsening of disease, an abnormal laboratory finding considered by the investigator to be clinically significant. Laboratory tests that deviate significantly from the normal range should be repeated with prior permission of the sponsor. If the abnormality persists and the investigator considers this a clinically significant abnormality, then efforts should be made to ascertain the etiology. If the abnormality is increasing, particularly if it was not there at baseline, the Director of Clinical Investigation should be notified.

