EpiCeram, a marketed product, is a three lipid emollient that has been shown to improve barrier structure and function, reduce skin pH, helps restore the microbiome components toward normal, improve immunological function and reduce symptoms associated with disrupted skin surfaces (Elias 2014, Elias 2019 and Kircik 2014). In contrast, some readily available over the counter skin care products may actually increase barrier dysfunction and aggravate skin disease (Li 2017, Elias 2019).

2. Hypotheses

- a. The signs and symptoms of skin irritation secondary to extensive use of PPE will be accompanied by measurable defects in skin barrier structure and function.
- b. EpiCeram will improve measurements of skin barrier integrity.
- c. Signs and symptoms of skin irritation will improve after one month of EpiCeram use.
- d. Improvement of skin barrier function will restore reduce skin colonization by pathogenic bacteria.

3. Study design

This will be a one (1) month, open label study. Subjects must be HCW who have used face and hand PPE at least four (4) days a week for a minimum of one (1) month (or, depending on shift work, at least 24 hours/week) and who have new (after March 1, 2020) symptomatic skin irritation on the hands and/or face. No change to required hand washing protocols or other protective measures will be required.

At Visit 1, Screening the study will be explained and an informed consent document (ICD) signed. Subjects will be entered into the electronic data capture (EDC) system using a direct data capture (DDC) tablet. Subjects will complete an overall skin irritation assessment on 0-10 scale where 0 = none and 10 = worst. If it is equal to or greater than 4, the subject may proceed to

enrollment provided all other inclusion and exclusion are met. If the subject has not used any lotions and emollients for the previous one (1) week on the face and hands, washout is not necessary, and Baseline visit activities may be performed at the Screening visit. Subjects requiring washout, will refrain from using any lotions and emollients for one (1) week between Visits 1 and 2 and then, for the duration of the study. Visit 2 (Baseline) will occur seven (7) days after Visit 1.

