At Visit 3 (Final), 28 days later subjects will complete an overall skin irritation assessment on a 0-10 scale where 0 = none and 10 = worst. Subjects will complete skin symptom scales of pain, redness, dryness, roughness, itching and cracking on a scale on a 0-10 scale where 0 = none and 10 = worst. Photos, skin function and laboratory testing will be in the same location as Visit 2. Photographs: Digital 3D photographs will be taken of the face and back of the hand. The face photo will be a two (2) inch by three (3) inch area of the cheek without identifying features. The hand photo will be the worst area of involvement as selected by the subject.

Skin Function Testing: Measurements of transepidermal water loss (TEWL) with stratum corneum hydration (SCH) and surface skin pH will be taken on the dominant hand on the dorsum of the 3rd and 4th metacarpal phalanges.

Laboratory Testing: Two types of specimens will be obtained; a swab and tape stripping. A single skin swab for bacterial qPCR will be obtained from the palm of the dominant hand. Non-invasive tape stripping of surface cells (3 strips/sample) will be performed at 2 sites; on the web between the 3rd and 4th metacarpophalangeal (MCP) joints on the dorsum of the dominant hand

for antimicrobial peptides (AMP) and three (3) strips/sample from the web between the 2^{nd} and 3^{rd} MCP joints on the dominant hand for free fatty acids. See the manual for detailed instructions on specimen collection. The subject will then be directed to apply EpiCeram to the hands (wrist to fingertips, front and back) and face at least three (3) times daily (about every 8-10 hours), more often if the subject wishes. The investigator will assess the subject' Response to Therapy on a scale of 1-5 with 1 = no response and 5 = best response. Subjects may then be discharged from the study.

4. Primary endpoints

- a. Change in patient reported outcome of overall face and hand skin irritation symptoms from baseline to Day 28, of at least 2 points on a 0-10 point scale where 0 = none and 10 = worst.
- b. Change in any two of the following specific skin irritation symptoms of at least 2 points on a 0-10 point scale where 0 = none and 10 = worst.
 - 1. pain
 - 2. redness
 - 3. dryness
 - 4. cracking
 - 5. roughness
 - 6. itchiness
 - 7. overall skin irritation

5. Secondary endpoints

- a. Reduction from baseline to Day 28 in pH
- b. Reduction from baseline to Day 28 in TEWL

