12.0 Study Withdrawal

Subjects may be withdrawn from the study for one or more of the following reasons.

- a. Request for withdrawal by the subject for any reason whether or not related to an AE.
- b. Lost to follow-up.
- c. Noncompliance with the protocol.
- d. Unacceptable adverse event. In this case the decision to remove the subject from the study may be made by the subject, the investigator or Primus.
- e. Determination by the investigator or Primus, that, withdrawing from the study is in the best medical interest of the subject.
- f. Administrative reasons such as early termination of the study.
- g. Treatment failure requiring an increase or addition of concomitant medication (s) or the use of any excluded medication.
- h. If the subject is discontinued prior to receiving the first dose of study product AEs and SAEs will be collected until the termination visit. If the subject has received study medication AEs and SAEs will be collected until the termination visit or until 30 days after the last dose of study product, whichever is later All AEs and SAEs must be followed until resolution or stability.

According to FDA and the Declaration of Helsinki a subject in a clinical trial has the right to withdraw at any time and for any reason without prejudicing his/her future medical care at the investigative site. In the case of early withdrawal of a subject, the investigator should make all reasonable efforts to have the subject attend a termination visit and document all details of the early termination on the appropriate data collection tool/CRF.

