14.8 Deaths

All deaths, regardless of cause, that, occur between the time a subject signs an informed consent document and the final study visit or 30 days after the last dose of study product, whichever is longer, must be reported to Primus by telephone with a follow-up fax within 24 hours of the investigator becoming aware of the death. This applies whether or not the

subject has received study product and whether or not the study product is thought to be causally related to the death. It is the investigator's responsibility to obtain all relevant medical records and autopsy reports and forward them to Primus as soon as possible.

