Appendix II

Schedule of Events

VISIT	V1	V2	V3
WEEK	Screen	Baseline**	DAY 28**
Window	-7 d	+/- 2d	+/- 2d
Informed Consent/Photo Consent	x		
Inclusion/Exclusion	x		
Demographics	x		
Current Face & Hand Treatment	X		
Medical History of Skin Disease	x		
Overall symptom rating	X	X	X
Skin symptoms rating		X	X
Photos of face and hand*		X	X
TEWL and SCH face and hand*		X	X
Skin pH face and hand*		X	X
Swab of dominant hand*		X	X
Tape Strip dominant hand*		X	X
Subject Response per Pl			X
Dispense Product		X	
Collect Product			X
Adverse Events		X	X
Changes to skin care		X	X

* Perform in the order listed. ** Instruct subject to stop washing hands and face for 2-hours prior to visit.

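### The adverse-event window runs to 30 days after the last dose, but the last scheduled assessment is Visit 3 at Day 28, and the Visit 3 text conflicts on when dosing ends

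*Combined protocol and SAP*

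**What the plan says.** **The window.** Section 14.1 (Definition of Adverse Event) has adverse-event data "be collected from that point until the end of the study or 30 days after the last dose of study product, whichever is longer"; the starting point is signature of the consent document. Section 12.0(h) (Study Withdrawal) sets the same limit for those who leave early after receiving product: "If the subject has received study medication AEs and SAEs will be collected until the termination visit or until 30 days after the last dose", taking the later of the two dates.

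**The schedule.** Visit 3 is the final visit, 28 days after baseline; Appendix II allows 2 days either side. Adverse events are assessed at baseline and at Visit 3 (Sections 11.2(b) and 11.3(b), and the adverse-events row of Appendix II). Section 3 closes the Visit 3 description with "Subjects may then be discharged from the study". No visit, call or message follows.

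**Dosing at Visit 3.** The Visit 3 text in both the synopsis and Section 3 reads "The subject will then be directed to apply EpiCeram to the hands" and the face, three or more times a day, with no end date. The procedure list in Section 11.3 has no application step. Appendix II has a row headed "Collect Product", marked at Visit 3 only.

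**The concern.** The plan states a safety window in one place and a contact schedule in another, and the schedule stops about 30 days before the window does. Adverse events are the only safety measurement listed, in the synopsis and in Section 9. If nobody asks subjects about events after Visit 3, what is found in that period depends on what they volunteer or on what the site happens to learn. Sites may also apply the window differently.

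The second problem concerns the clock itself. The window is counted from the last dose, yet the documents conflict on whether application ends at Visit 3. No final-visit step records the date of last application.

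**Working it through.** The plan gives no figure of its own for this point, so there is nothing to reproduce. The check is day arithmetic, with baseline as Day 0.

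**Inputs**
- Tail after last dose: 30 days (Sections 12.0(h) and 14.1).
- Visit 3: Day 28, or Day 26 to 30 across the window (Appendix II).
- Consent to baseline: 0 days if screening and baseline fall on the same day; 7 days with washout (Section 3); up to 9 days if the 2-day baseline window in Appendix II is used.
- Assumption: the last dose is on the day of Visit 3.

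**End of the window** = day of last dose + 30.
- Visit 3 on Day 28: 28 + 30 = Day 58.
- Across the visit window: 26 + 30 = Day 56, to 30 + 30 = Day 60.

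**Share of calendar days with no scheduled contact to come** = 30 / (days from consent to Visit 3 + 30).

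| Case | Calculation | Share |
|---|---|---|
| Same-day screening, Visit 3 on Day 26 | 30 / (26 + 30) = 30/56 | 54% |
| Same-day screening, Visit 3 on Day 28 | 30 / (28 + 30) = 30/58 | 52% |
| Same-day screening, Visit 3 on Day 30 | 30 / (30 + 30) = 30/60 | 50% |
| 7-day washout, Visit 3 on Day 28 | 30 / (7 + 28 + 30) = 30/65 | 46% |
| 9 days to baseline, Visit 3 on Day 30 | 30 / (9 + 30 + 30) = 30/69 | 43% |

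Section 11.1 puts screening at least a week before baseline when washout is needed and gives no upper limit, so the lowest share could be smaller still. The 30 days themselves do not change.

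**If application continues after Visit 3**, the end of the window moves day for day. The documents give no duration. Assuming 7, 14 or 30 further days of use, it falls on Day 28 + 7 + 30 = 65, Day 28 + 14 + 30 = 72, or Day 28 + 30 + 30 = 88.

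**Early withdrawals.** Section 13.0 asks for a termination visit at the next scheduled appointment or within 14 days. If product stops when the subject decides to leave and the visit is 14 days later, 30 − 14 = 16 days of the window remain with no planned contact.

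**The case against.** The strongest reply is that the plan already has routes for late events. Section 14.6 allows follow-up beyond the end of the study, does not let a site close with an event outstanding, and asks for serious events after the study that may be related to product. Section 14.2 requires all serious events to be reported whatever their cause. Section 16.5 requires a telephone log, so contact outside visits is foreseen. The product is already marketed, and Section 14.11 describes it as a device whose occlusive ingredients prevent systemic uptake. Few serious events may therefore be at stake.

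Much of this stands, and it limits the weight of the point. It does not close the gap. Section 14.6 follows events already known and takes in possibly related serious events; it plans no contact to find new ones. The reporting duties in Sections 14.2 and 14.5 depend on the site learning of the event.

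It can also be said that the Visit 3 application sentence nearly repeats the Visit 2 wording and may be carried-over text, since Section 11.2 dispenses one unit at baseline and Appendix II shows no dispensing at Visit 3. That is plausible. But the sentence stands in two places, and the documents do not say that it is an error.

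A reader might infer that the death-reporting rule in Section 14.8 has the same defect, because deaths between consent and "the final study visit or 30 days after the last dose of study product, whichever is longer, must be reported to Primus by telephone". It does not: the duty is triggered when the investigator becomes aware of the death, so no scheduled contact is needed to make it workable.

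**Conclusion.** The inconsistency is real. For every completer (50 planned, of 55 enrolled), the last 30 days of the stated window have no scheduled ascertainment, assuming the last dose is on the day of Visit 3. This is about 43% to 54% of the window's calendar days, depending on washout and visit windows. New non-serious events, and serious events that the site does not hear about, are likely to be under-counted. Separately, the instruction to apply product at Visit 3 conflicts with its collection at that visit, so the date that starts the clock is contradictory. If application continues, the end of the window cannot be worked out from the documents.

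Three stronger readings are not supported:
- That about half of all adverse events would be missed. The percentage counts days, and the documents give no event rate.
- That the study report will claim complete 30-day collection. No passage says what the report will state about completeness.
- That the efficacy results are affected. The gap does not touch the endpoints, the sample size or the planned tests.

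The point is worth correcting because the mismatch affects the trial's only safety measurement and the change is small.

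**What to change.** 1. Reconcile Sections 11.3, 12.0(h) and 14.1 with Appendix II so that the adverse-event window and the scheduled contacts agree. The preferred way is one remote adverse-event contact at the end of the 30-day window, added to Appendix II and Section 11.3, with matching wording for withdrawn subjects. The cost is one short call or e-mail per subject, at most 55 in all.
2. If no contact is added, state in Section 14.1 and in the report that events after Visit 3 are captured by spontaneous report only. This costs wording alone, but leaves ascertainment in that period weaker than before Visit 3.
3. Reconcile the Visit 3 application text in the synopsis and Section 3 with product collection in Appendix II, the Section 11.3 procedure list and discharge. Which instruction is right is for the sponsor and investigator to settle; this review takes no position.
4. Record the date of last application for each subject, so that the 30-day clock starts from one documented date. This needs one field on the data collection tool.
5. Leave the Section 14.8 death-reporting window unchanged. Shortening it would resolve no conflict.

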14.2 Serious Adverse Events

SAEs require special attention, management and documentation. All SAEs must be reported to Primus within 24 hours **whether or not** they are considered by the investigator to be related to the study agent (s). Although cancer is no longer considered an SAE by the USFDA, Primus requires notification of such diagnoses within 48 hours of the time the investigator first learns of the event. An SAE is any medical event that:

- a. results in death
- b. is life threatening—the investigator believes the subject's life is in immediate danger. This does not include events that, had they been more severe, might have been life threatening.
- c. requires in-patient hospitalization or prolongation of an existing hospitalization.
- d. results in permanent disability.
- e. is a congenital anomaly or birth defect.
- f. requires medical or surgical intervention to prevent one of the outcomes above.

14.3 Severity of Adverse Events

The investigator must rate every AE for severity according to the following guidelines:

- mild does not interfere with daily activities.
- moderate discomfort and/or dysfunction enough to interfere with, but not prevent, daily activities
- severe significant impairment of ability to perform daily activities.

14.4 Assessment of Causality

Investigators will be responsible for determining the relationship of the study product(s) to the AE and will record their conclusions on the data collection tool, adverse event page. It is recognized that causality often cannot be established with certainty. Investigators must use their best clinical judgment keeping in mind the following questions:

- a. Was study product administered?
- b. What was the temporal relationship between the administration of study product and the AE? Was this consistent with the nature of the AE?
- c. Was there another obvious or possible cause for the AE?
- d. Was the AE consistent with the known effects of the study product?
- e. Were there any features of the subject's clinical state, concomitant medications or diseases or environmental factors that could have caused or modified the AE?

- f. Did the AE resolve, improve, remain stable or worsen after the study product was stopped or the dose reduced?
- g. If the subject was re-exposed to the study product (re-challenge), did the AE recur, worsen or remain unchanged? Re-challenge should be attempted only after careful consideration and only after discussion with Primus.

Investigators should use their best clinical judgment and the guidelines above to assign all AEs and SAEs to one of the following four categories:

Not Related	Those AEs for which other etiologies can clearly and conclusively be defined.
Possibly Related	Those events for which other etiologies cannot be clearly
	demonstrated, and for which a relationship to the study agent cannot be positively excluded
Probably Related	After careful scrutiny of the available medical facts, there is
	a reasonable, but inconclusive, certainty that the event is
	related to the study product.
Definitely Related	After careful medical evaluation there is little or no doubt
	that the study product is the direct etiologic cause of the
	AE. This situation is most commonly seen when an AE
	recurs after re-challenge with study product.

14.5 Reporting Serious Adverse Events

SAEs must be reported to Primus by telephone or, if from a non-U.S. site, by e-mail within 24 hours from the time the investigator first learns of them. This should be followed by a faxed report outlining the details of the event and the investigator's assessment of the severity and relationship of the event to the study agent. All SAEs will be reported on both the AE and SAE pages of the data collection tool/case report forms. In addition:

- a. A new SAE form must be completed and faxed to Primus within 24 hours.
- b. Follow-up SAE forms must be completed and faxed to Primus whenever new information becomes available about the event.
- c. A final SAE report must be completed and faxed to Primus when the event has resolved or its consequences have stabilized and all relevant information (including hospital records, laboratory and pathology reports, autopsy reports, etc.) have been received. It is the responsibility of the investigator to obtain copies of all relevant information in a timely manner.
- d. It is the responsibility of the investigator to determine the severity and causality of the SAE.
- e. The initial SAE report and all subsequent reports must be retained in the subject's study file together with a telephone log of all contacts with Primus and the subject. These should be recorded at the time of the conversation, dated and signed

by the investigator or his/her representative and should include the name of the person with whom the conversation was held.

Telephone contact should be made with [name], Director Clinical Development [contact] (office) [contact] (mobile) [contact]

If [name] is unavailable contact: [name], BSN, Project Manager [contact] [contact] (cell) [contact]

Primus will review all SAEs with the investigator and a decision will be made regarding the need for further action. Primus' primary concern will be subject safety, both for the subject having the event as well as for the other subjects in the study. If, after detailed review, it is determined that a subject safety issue exists, Primus will notify all investigators participating in any trial with the same study product and the IRB(s) overseeing those trials, and may require one or more of the following:

- a. Discontinuation or suspension of the study
- b. Modification of the protocol
- c. Modification of the informed consent document to reflect additional risk(s) to be signed by current and future subjects.
- d. Addition of newly discovered adverse events to the investigator's brochure

14.6 Follow-Up of Adverse Events

All adverse events, whether serious or non-serious, must be followed until resolution or stability. This follow-up may extend beyond the end of the study. Primus considers AE follow-up to be part of a study. Therefore, a study cannot be closed at an investigative site if an AE is outstanding. Any serious AE occurring after the conclusion of a study must be reported to Primus if the investigator thinks the event *may* be causally related to the study agent.

